#### 7.3 DESIGN

#### 7.3.1 Design type:

This is a prospective, randomized, controlled, observational pilot study analyzing both providers' and patients' perceptions and responses to the DNA Insight test. For this study there will need to be a total of twelve provider groups to be enrolled and 4-8 of each provider's patients will be enrolled in the study. Enrollment will continue of providers until up to 12 providers and 48 patients have been enrolled in the study. Therefore twelve to sixteen military health system primary care providers will need to be consented due to withdrawal of providers prior to

Page 13 of 34

Protocol Title: Patient and provider confidence and satisfaction with the clinical use of CYP genetic variability analysis to guide analgesic treatment: A randomized, controlled pilot study using the Pain

Medication and Mental Health DNA Insight $^{\text{TM}}$  test.

Initial Date Submitted: 02/10/2015 Revision Date: 31 August 2016

referring patients. A total of 48 patients will be enrolled, 4-8 patients for each of the actively enrolled providers (12- 16 providers and 48 patients total). Each provider's patients will be randomized into delayed treatment (Group A) or immediate treatment (Group B) at a 1:1 ratio. Each participating provider will agree to order and interpret a Pain Medication and Mental Health DNA InsightTM test. Results for patients in Group A will be given to the provider with a 3 month delay. Those in the 3 month delay will serve as a comparison group for the period prior to receiving intervention. Results for patients in Group B will be given to the provider without delay, 2-3 weeks after saliva sample collection. The provider will use the results of the Pain Medication and Mental Health DNA InsightTM test to evaluate whether changes of medications are indicated based on the individual patient's genetic profile. A measure of the provider's certainty, confidence, satisfaction, perception of care and global impression of change will be assessed at baseline, prior to obtaining the test results, and after obtaining the test results, as outlined in the data collection section. Patients' pain related self-reported outcomes, certainty, confidence and satisfaction will be assessed at baseline, prior to obtaining the DNA InsightTM test results, and after receipt and implementation of the test results, as described in the data collection section of the protocol.

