- ♦ The head nurses/nursing staff of each enrolled provider will be briefed on the study, inclusion/ exclusion criteria and their role in recruitment. The nurses will be ask to give potential candidates they think may qualify for the study a patient ad (Appendix 2).
- ♦ A poster that looks similar to Appendix 2 will be placed in each recruiting clinic's lobby to expose potential candidates to the idea of the study. Contact information is provided for the potential candidate to contact the research team. The poster asks for interested patients to fill out an information card with their name, phone number, and provider name. The cards can be placed in a solid box. The research coordinator will pick up all cards once a week. All patients will be called. Patients with providers not enrolled in the study will be thanked for their interest and told they cannot participate.
- ♦ The research coordinator will have access to consented providers' patient list through AHLTA. Pain patients will be identified daily through the "reason for visit" column. The patient will be sent a recruitment letter stating information about the study. A member of the research team will then call the potential patient about 4 days after sending the letter to see if the subject is interested and qualifies for the study. If the provider already has 4 patients participating or feels that patient would not be a good candidate the patient will be informed they do not qualify and they will be thanked for their time.
- ♦ Consented providers will be sent an email to inform them that their pain patients will be sent letters to see if they are interested in the study. Providers will be informed if their patient is interested in the study.
- ♦ A screen excel will be kept on a password protected computer. The spreadsheet will be used to keep track of patients who have been sent letters. There will be no PHI in the spreadsheet. Patient initials, date of sent letter, date of call and if they agreed to participate will be recorded.
  - ♦ The study coordinator will meet with potential subjects prior to one of their scheduled appointments, explain risks/benefits of study, and obtain informed consent for inclusion in the study. These potential subjects will have the opportunity to review the consent via email prior to their meeting with the study coordinator if they choose.

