  - ♦ Once consented; subject will be allocated into one of the two study groups based on a table of randomized numbers. Subjects' demographic information such as age, gender,

Protocol Title: Patient and provider confidence and satisfaction with the clinical use of CYP genetic variability analysis to guide analgesic treatment: A randomized, controlled pilot study using the Pain

Medication and Mental Health DNA InsightTM test. Initial Date Submitted: 02/10/2015

Revision Date: 31 August 2016

race, email and phone numbers will be collected. (Appendix C2). This will also list their provider study ID number as well. Prior to the first study-related visit with the provider (Visit 0) the subject will be asked to complete the Defense and Veterans Pain Rating Scale (DVPRS) with Supplemental Items (Appendix D), the Brief Pain Inventory Short Form (BPI-SF) Perception of Relief Item over past week (Appendix E), Patient Reported Outcome Measurement Information System (PROMIS) short forms for pain interference (Appendix F), depression (Appendix G) and anxiety (Appendix H), the Patient Perceptions of Care (Appendix I), and Patient Global Impression of Change (Appendix J). The subject will be provided with a list of common opioids and NSAIDs (Appendix K) and be asked their current medications both prescription and OTC/ alternative treatments. (Appendix L).

- ♦ At Visit 0 a saliva sample will be collected by the study coordinator and labeled with a study ID number assigned specifically to that subject and all the samples for that day will be shipped to Pathway genomics following IATA (international air transport association) shipping regulations. Saliva is collected on all patient volunteers regardless of which group they are in. The DNA/ saliva sample will be destroyed 60 days after collection by the Pathway Genomics lab.
- ♦ After the first study-related visit with the provider (Visit 0) the subject will be asked to complete the patient certainty, confidence and satisfaction surveys (Appendix M). This survey will be provided by email.
- ♦ After Visit 0 with the subject the provider will be asked to complete the Provider Perception of Care (Appendix N), the Provider Global Impression of Change (Appendix O), and Provider Certainty, Confidence and Satisfaction surveys (Appendix P). These surveys can be hand-delivered to provider or provided over email.

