- ♦ A member of the research team will query AHLTA to confirm the subject's current analgesic medication regiment at the time of enrollment. All analgesics will be documented as a total daily dose and all opioids will be converted to daily oral morphine equivalents using the Hopkins Opioid Program (www.hopweb.org). These data will be entered into the CRF [(Case Report Form) (Appendix L). A medication will be classified as an analgesic according to (Appendix Q).
- ♦ If the subject is randomized to Group A, there will be a 3-month wait period before the provider will receive the subject's DNA test result. During this time the patient will be scheduled for monthly visits (Visit 1, 2, and 3) with the provider. Each visit will be at least 1 month in advance or as the clinic allows. During these visits the medications may be changed or adjusted according to routine care. Before each visit the subject will be

Protocol Title: Patient and provider confidence and satisfaction with the clinical use of CYP genetic variability analysis to guide analgesic treatment: A randomized, controlled pilot study using the Pain

 $\label{eq:medication} \mbox{Medication and Mental Health DNA Insight}^{\mbox{\scriptsize TM}} \ \ \mbox{test.}$ 

Initial Date Submitted: 02/10/2015 Revision Date: 31 August 2016

asked to complete surveys of Appendix D, E, F, G, H, I, and J. After each visit the subject will be asked to complete survey of Appendix M. After each visit the provider will be asked to complete surveys of Appendix N, O, and P.

- ♦ A report for the subjects study ID number will be returned to the provider within 1-3 weeks of saliva sample collection for subjects in the Group B, and after the 3-month wait period for Group A. The test report has only the subject's study ID on it, so the study coordinator will match the name of the subject with the subject study ID once it returns, so the provider is aware of the name of the subject. The report will be hand-delivered to the Primary Care Manager (PCM) by the study coordinator for use by the PCM at his/her discretion The provider will keep a copy of the results in a research folder for their use at other study visits. The provider will be informed in the ICF and when results are handed to them that the test results are not to be placed in the patient's medical record or shared with another provider.

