When conducting a MLM analysis, the assumption is that there is a nested structure, and particularly for event-based studies, time (level 1-microlevel) will be nested within the patient (level 2- individual). For this study there are 12 provider groups with 4 patients nested within the groups, hence this could be cast as a 3-level model (time nested within patient nested within provider). However, one caveat is this is a very small sample size for MLM, and power may be a significant issue. The viability of increasing the sample size or aggregating levels (if deemed appropriate insofar it does not compromise the integrity of the design) will be explored. A sequence of models will be examined, with the unconditional means model (no predictors) as the starting point, serving to compute the unconditional intraclass correlation coefficient (ICC), and hence capturing the extent of between-patient variability. Subsequent models will entail adding a variable that captures time, and then at the macro-level introducing the grouping (experimental vs. control) variable. If deemed appropriate, all time-invariant and time-varying predictors will be testing for significance ( $\alpha = .05$ ) and moreover, the stochastic parameters (i.e., variance components) will also be examined:  $\underline{u}_0$  and possibly  $\underline{u}_1$  where  $\underline{u}_0$  is the random coefficient for the intercept (i.e. initial basis) and  $u_i$  is the random coefficient for the slope. For the single-item ordinal-level outcomes the cumulative logit link function will be employed using residual maximum likelihood (REML) as the default estimator (otherwise the identity link function will be used for continuously measured outcomes).

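### Providers can decline candidates without a stated reason while learning earlier arms, and no concealment is described; if 1:1 is kept exactly within four patients, up to 70.8% of allocations could be guessed

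*Combined protocol and SAP*

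**What the plan says.** **Entry.** Under 7.3.4, enrolled providers identify and refer candidates from their own panels. For patients found through the appointment list and sent a letter, 7.3.4 adds "Providers will be informed if their patient is interested in the study", and a candidate is turned away "If the provider already has 4 patients participating or feels that patient would not be a good candidate". That judgement is separate from the written patient inclusion and exclusion criteria in 7.3. The screening spreadsheet for letter recruits holds initials, letter date, call date and whether the patient agreed; it has no field for a provider's reason.

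**Allocation.** Section 7.3.1 states "Each provider's patients will be randomized into delayed treatment (Group A) or immediate treatment (Group B) at a 1:1 ratio". Section 7.3.4 says that after consent the "subject will be allocated into one of the two study groups based on a table of randomized numbers", and mentions the baseline forms next. Neither section gives a block rule, a holder of the table or a step that hides the next entry.

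**Knowledge of earlier arms.** Under 7.3.4, "The report will be hand-delivered to the Primary Care Manager (PCM) by the study coordinator", who first matches it to the patient's name. This happens at 1-3 weeks for Group B (2-3 weeks in 7.3.1) and after the 3-month wait for Group A.

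**Numbers.** Section 8.0: "For this study there are 12 provider groups with 4 patients nested within the groups". Section 7.3.1: "4-8 of each provider's patients will be enrolled in the study" and "A total of 48 patients will be enrolled".

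**The concern.** A report on a named patient shows Group B, and no report by about week 3 shows Group A. A provider who enrols patients over a longer span therefore learns earlier arms while still able to influence who enters next. If balance is enforced within a handful of patients, the remaining places can be worked out by counting. A provider who, even without intent, favours different patients according to the arm expected would make the groups differ at entry.

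The same providers complete the ratings of certainty, confidence, satisfaction, perception of care and change that answer the first research question in 7.1, and the patient outcomes are self-reports. Because no reason for a decline is recorded, selection of this kind could not be detected afterwards.

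Provider knowledge of the arm after allocation is part of the design and is not the complaint. The complaint is avoidable foreknowledge before entry.

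**Working it through.** **Inputs from the plan:** 1:1 within provider (7.3.1); four patients per provider (8.0, and the cap in the 7.3.4 letter route); 48 patients in total (7.3.1), so 24 per group; alpha .05 (8.0, sidedness not stated). **Assumption:** patients entered when Group B or Group A is expected differ from average by plus or minus e, with e = 0.1 to 0.25 SD.

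1. *The plan's own figure.* 12 x 4 = 48, as stated. 12 x 8 = 96 and 16 x 4 = 64 do not give 48, so four per provider is the working number.

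2. *Predictability with exact 2:2 and all earlier arms known.* There are C(4,2) = 6 equally likely orders, and the best guess is the arm that is behind.
   - Patient 1: 1/2.
   - Patient 2: 2/3.
   - Patient 3: the first two match with probability 1/3 (then certain), otherwise 1/2; 1/3 x 1 + 2/3 x 1/2 = 2/3.
   - Patient 4: 1.
   - Sum 2.833; 2.833/4 = 70.8%. The Blackwell-Hodges formula agrees: 2 + (16/6 - 1)/2 = 2.833.
   - Certain allocations: (1/3 + 1)/4 = 1/3, or 16 of 48 expected.

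3. *When the latest arm is still unknown.* Patients 1 and 2 are guessed at 1/2 and patients 3 and 4 at 2/3. The sum is 2.333, or 58.3%.

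4. *Exact 4:4 within eight patients.* 66.6% on average, with 20% certain.

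5. *Unrestricted randomization.* Guessing stays at 50%. With four patients, 2:2 occurs in 6/16 = 37.5% of providers and all four fall in one arm in 2/16 = 12.5%, so the within-provider ratio in 7.3.1 would often fail.

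6. *Entry difference, upper case.* Correct minus incorrect guesses per provider = 2 x 2.833 - 4 = 1.667. Each group has two patients, so the difference is e x 1.667/2 = 0.833e: 0.08 SD at e = 0.1 and 0.21 SD at e = 0.25. With the latest arm unknown (step 3), the factor is (2 x 2.333 - 4)/2 = 0.333, giving 0.08 SD at e = 0.25.

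7. *Scale.* The simple standard error with 24 per group is sqrt(2/24) = 0.29 SD, and 0.21/0.29 is about 0.7.

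8. *Simulation* (40,000 trials of 12 x 4, no true effect, unadjusted two-sided t-test at 0.05). Exact 2:2 with e = 0.25 gives a mean shift of 0.21 SD and a type I error of 10.4%. With one 24:24 list over all 48 patients, or with simple randomization, and providers counting only their own patients, the mean shift is about 0.01 SD and type I error stays near 5%. Even at e = 1 SD the shift under those two schemes is at most 0.04 SD.

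**The case against.** **A reader might infer that the veto lets a provider hold a difficult patient for a likely Group B place.** The text does not support this. A declined patient is turned away, not deferred, and the clause sits only in the letter route. Nor does the plan say that providers put patients forward singly. Candidates also come from nurses, lobby cards, associate investigators' suggestions and the coordinator's daily screening. Influence on timing would have to come through the provider's own referrals. What stands is that providers can refer selectively and can filter out, without a recorded reason.

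**A reader might take 70.8% as a property of the plan, or the entry difference as a full standard error.** Neither follows. The first needs exact 2:2 and known earlier arms, and the documents state neither. The second fails because the upper-case shift is about 0.7 of the simple standard error, and only if every provider steers whenever the counts allow.

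**Baseline adjustment would help.** It would remove part of the shift. Section 8.0 includes baseline among the repeated measures but names neither a baseline-adjusted contrast nor a group-by-time term, so how much is removed depends on a choice still open.

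**Provider approval has a basis.** Section 3.0, item A, asks for the primary care provider's approval where appropriate. That stands: the right to decline should remain.

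**The stakes are limited.** This is a hypothesis-generating pilot (7.1), its first two aims examine trends (7.2), and every patient's provider receives the results in the end, which weakens any motive to steer. Even so, 8.0 plans tests at .05 and 7.1 intends the data to feed a fully powered trial, so a biased contrast would carry forward.

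**Conclusion.** The concern holds as a risk that the plan leaves open. Providers influence entry, can learn earlier arms, and face no described concealment. The size is conditional: guessing reaches at most 70.8%, with one third of allocations certain, if 2:2 is exact and all earlier arms are known. It is about 58% if the latest arm is unknown, and 50% under unrestricted randomization, where the ratio in 7.3.1 would often not be met. Under assumed steering of 0.1-0.25 SD, the upper-case entry difference is 0.08-0.21 SD before any baseline adjustment.

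The documents do not show that steering occurred, and they do not say who holds the table, so it should not be inferred that the coordinator does. The gap is worth closing because it is cheap to close, not because it invalidates the pilot.

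**What to change.** In 7.3.4:

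(a) Base entry on the written inclusion and exclusion criteria in 7.3. A provider may still decline a candidate, consistent with 3.0 item A, but only with a reason logged before allocation is requested. Where feasible, do this in one review of the candidate list before that provider's first patient is allocated. Apply the same log to provider referrals.

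(b) Have the outside statistician already named in 8.0 generate and hold the sequence. Reveal each arm, for example through REDCap, only after consent and baseline forms are recorded. Waiting should cost little, since the first report is not due until 1-3 weeks after the saliva sample.

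(c) Say whether balance is forced within provider. Hiding the list does not stop a provider from counting within a 2:2 block. Either avoid exact 2:2, for example with one concealed list over all 48 patients, varying block sizes and provider in the model, or keep within-provider 1:1 and rely on the advance review in (a). The simulation above covers a single 24:24 list; with short blocks, some counting returns if one provider's patients enter consecutively.

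Reconcile four with 4-8 patients per provider, and 1-3 with 2-3 weeks to report, because both affect what can be deduced.

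**Cost:** protocol wording and set-up of an allocation step in software the study already uses. Providers lose an unexplained veto, and exact balance within provider may be lost.

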# **7.2 SPECIFIC AIMS/SIGNIFICANCE:** Specific Aims

- 1. Examine trends in provider decisions in prescribing analgesics and modifying analgesic treatment plans and provider outcomes for satisfaction, certainty and confidence in dosing of analgesics with and without access to Pain Medication and Mental Health DNA Insight TM genetic testing results.
- 2. Examine trends in patients' satisfaction, certainty and confidence in dosing of analgesics between patient groups whose providers had access to Pain Medication and Mental Health DNA Insight TM genetic testing results and those whose providers did not have access to the genetic information.
- 3. Compare patient-reported pain and mental health outcomes between patient groups whose providers had early access to Pain Medication and Mental Health DNA Insight TM genetic testing results to those who had delayed access in the control period and subsequently following later access to the results.

The general aim of this pilot study is to assess the utility of a test that analyzes the DNA of chronic pain patients to determine their metabolic response to common analgesics, anti-depression and anxiolytic medications, to improve provider and patient confidence and satisfaction with the pain treatment plan. The results of the DNA analysis will help guide providers to change or continue the current analgesic regimen. This concept is known as "personalized" or "precision" medicine - the ability to treat patients based on their genetic profile in order to maximize therapeutic effect and minimize or eliminate unwanted side effects.

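### Baseline ratings follow allocation with no stated withholding of the group, and the model leaves a provider effect optional although patients are randomised within provider (minor)

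*Combined protocol and SAP*

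**What the plan says.** **Order of events.** Section 7.3.4 allocates directly after consent: "Once consented; subject will be allocated into one of the two study groups based on a table of randomized numbers". The ratings follow. "Prior to the first study-related visit with the provider (Visit 0) the subject will be asked to complete" introduces patient forms D–J. Patient form M is emailed after the visit, with no return date given. For providers: "After Visit 0 with the subject the provider will be asked to complete the Provider Perception of Care (Appendix N", together with O and P. Sections 7.3.1 and 8.0 place the baseline before the test results or the intervention, not before allocation. The Visit 0 procedures do not differ by group; for the sample, "Saliva is collected on all patient volunteers regardless of which group they are in".

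**Randomisation within provider.** Section 7.3.1: "Each provider's patients will be randomized into delayed treatment (Group A) or immediate treatment (Group B) at a 1:1 ratio". The only mechanism given is the table in section 7.3.4.

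**Patients per provider.** Section 7.3.1: "A total of 48 patients will be enrolled, 4-8 patients for each of the actively enrolled providers". On the letter-and-call route in section 7.3.4, a patient is told that he or she does not qualify "If the provider already has 4 patients participating or feels that patient would not be a good candidate". Section 8.0 works with 12 provider groups of exactly 4.

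**Model.** Section 8.0 says that the data may be treated as time within patient within provider. It warns that the sample is very small for this and will explore merging levels if the design is not compromised. The model sequence that it spells out has between-patient variability and a random intercept and possibly slope, with no provider variance. For the GEE comparison it does not say whether patient or provider is the cluster.

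**The concern.** Most of the outcomes are subjective: satisfaction, certainty, confidence, perceived care and self-reported pain. Patients and providers who know that a result is coming soon, or is three months off, may rate differently even at Visit 0. An unaffected baseline cannot be recovered later. Aim 3 in section 7.2 compares the groups over "delayed access in the control period and subsequently following later access to the results", so Visit 0 anchors a comparison with few time points.

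The provider issue is separate. The trial randomises within provider, and the same person completes forms N, O and P for all of that provider's patients. Ratings may therefore be correlated within provider. A model without a provider term leaves those differences in the residual and gives away precision that the design offers. Section 8.0 itself flags power as a possible problem.

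**Working it through.** **1. The plan's own count.** 12 providers × 4 patients = 48, which reproduces the stated total. The plan has no power calculation to reproduce. With 48 patients and 4–8 per provider, the number of active providers lies between 48/8 = 6 and 48/4 = 12, and 12 is possible only at exactly 4 each.

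**2. Is the group needed before the Visit 0 forms?** Sections 7.3.4 and 7.3.6 and Table 1 give the same Visit 0 in both groups: consent, saliva, forms. The groups first diverge when a Group B report reaches the provider, 1–3 weeks after the sample in section 7.3.4 (2–3 weeks in section 7.3.1). Nothing in the available text needs the group earlier. Because form M has no return date, a late baseline form could also be completed after a Group B report has arrived.

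**3. How much could a Visit 0 shift matter?** Its size is unknown, so only its leverage can be computed. Assumptions: equally spaced visits, complete data, a linear fit, and a shift of 1 unit confined to Visit 0 in one group.
- Visits 0–6: mean time 3, sum of squares 9+4+1+0+1+4+9 = 28. Slope change (0−3)/28 = −0.107 per visit, or −0.643 over six visits. Intercept change 1/7 + 9/28 = 0.464.
- Visits 0–3 alone (control period; the Visit 3 forms D–J come before the results are discussed): mean time 1.5, sum of squares 5. Slope change −1.5/5 = −0.30 per visit. Intercept change 1/4 + 2.25/5 = 0.70.

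So part of a Visit 0 shift would pass into the trajectory contrast, and more if the control period is fitted alone.

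**4. What does leaving out provider cost?** Inputs: 12 × 4, every provider split 2:2, 24 patients per group, total variance 1, provider ICC ρ. The documents give no ICC, so 0.1, 0.2 and 0.3 are assumed.
- True SE of a single-visit contrast: √((1−ρ)·2/24), because provider differences cancel.
- SE with provider ignored: about √(2/24).
- Ratio 1/√(1−ρ): 1.054, 1.118, 1.195.
- In a group of 24, 12 of the 276 pairs share a provider (12/276 = 1/23), so the sample variance averages 1 − ρ/23. The ratio becomes √((1−ρ/23)/(1−ρ)) = 1.052, 1.113, 1.187.

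| | ρ = 0.1 | ρ = 0.2 | ρ = 0.3 |
|---|---|---|---|
| SE overstated, simulated (20,000 runs) | 4.6% | 10.6% | 18.0% |
| Type I error, provider ignored | 3.8% | 3.1% | 2.1% |
| Type I error, provider as fixed effect | 4.9% | 5.1% | 5.1% |
| Slope contrast over 7 visits, type I error, provider ignored (6,000 runs) | 5.1% | 5.0% | 5.3% |

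Tests of level are conservative, not inflated. A constant provider difference drops out of each patient's slope, so slope contrasts are unaffected.

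**5. Is a provider term workable with about 12 providers?** In a single-visit model the provider variance is estimated as zero when F(11, 35) falls below 1/(1 + 4ρ/(1−ρ)). The probability is 26%, 11% and 4% at the three ICCs. A fixed provider effect uses 11 further degrees of freedom: 48−2 = 46 becomes 48−12−1 = 35, and the t cut-off moves from 2.01 to 2.03.

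**The case against.** **Silence in an incomplete text.** Section 7.3.4 gives the order of allocation, not of disclosure, and the diagrams, consent pages and appendices are not available. A reader might infer that the baseline ratings are biased. The documents do not support that; they support only that no available section protects these ratings. This part of the objection stands.

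**The leverage figures rest on convenient assumptions.** Group B's Visit 1 follows a report due within weeks, Group A's visits are monthly or as clinics allow, and section 8.0 expects unequal numbers of measures. An expectation effect might also persist. If it lasted through Visits 1–6 while Visit 0 was protected, the slope would move by +0.107 per visit, whereas a constant shift over all visits would leave it unchanged. This is correct, and the figures in step 3 should be read as illustration only. But a persistent effect is the ordinary bias of an unblinded comparison after baseline, not a reason to expose the baseline as well.

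**Within-provider balance is already stated.** This stands. A reader might infer from the random-number table that balance is left to chance. Under simple randomisation with 4 patients, only 6/16 = 37.5% of providers would split 2:2, and the chance of at least one provider among 12 with all patients in one group would be 1 − 0.875^12 = 80%. Those figures need a reading at odds with section 7.3.1, since such a table can also generate a blocked list. Only the mechanism is unstated.

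**Section 8.0 already recognises the provider level, and flexibility is sensible in a small sample.** This stands in part. The plan names the structure and warns about size, and step 5 shows that zero variances are quite possible. That argues for a stated fallback, not for leaving the term optional. A reader might also infer an inflated type I error, as when whole clusters are randomised. Step 4 shows the opposite for balanced splits.

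**Conclusion.** The point holds as a minor one, in three parts.
- **Timing.** Allocation precedes every baseline rating and no available section withholds the group. This is an avoidable risk whose size cannot be estimated.
- **Provider effect.** The analysis does not commit to the factor within which patients are randomised. The cost is precision in level contrasts: a single-visit SE overstated by about 5, 11 or 18%, given 2:2 splits and assumed ICCs of 0.1, 0.2 and 0.3. It is not bias, and slope contrasts are unaffected as long as provider differences are constant over time. These are single-visit figures, whereas section 8.0 plans repeated-measures models.
- **Clarification only.** The 1:1 ratio within provider is stated but its mechanism is not, and the three statements of patients per provider do not agree.

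Section 7.1 describes a pilot meant to generate hypotheses and preliminary data, and there is no power target to miss. This limits the consequences.

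**What to change.** **Section 7.3.4, timing.** Have forms D–J completed before allocation. Withhold the group from patient and provider until the Visit 0 forms M, N, O and P are returned, or until a fixed cut-off before the earliest Group B report (1 week in section 7.3.4), whichever comes first. Flag later forms as post-disclosure. Cost: protocol wording, one reminder and some late forms.

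**Section 8.0, model.** Make a provider effect the default for patient and provider outcomes, and do not aggregate over provider. State the fallback in advance:
- a provider variance estimated as zero is reported as zero;
- if a continuous-outcome model does not converge, provider enters as a fixed effect;
- if a cumulative-logit model does not converge, the two-level model is reported and declared as such.

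Cost: zero variances or non-convergence must be expected with about 12 providers; the fixed-effect fallback costs 11 degrees of freedom.

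**Sections 7.3.1, 7.3.4 and 8.0, clarification.** Say how 1:1 within provider is produced, and reconcile 4–8, stop at 4 and exactly 4 patients per provider. I do not propose a block scheme. Providers refer patients and can learn earlier allocations. With four patients and past allocations known, the best guess is right on average 70.8% of the time under fixed blocks of 4 (50, 67, 67 and 100% by slot). Mixed blocks of 2 and 4 give the same average (50, 83, 58 and 92%) and lose the guaranteed 2:2. Simple randomisation gives 50%. The choice is a trade-off for the investigators.
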